5.2 SAFETY ENDPOINTS

Adverse outcomes are primary endpoints in this study and they include the following categories defined by KCD-7 diagnosis codes and/or NHI procedure codes appearing in medical claims data after the index date.

- GI bleeding
I850, I983, K2211, K226, K228, K250, K252, K254, K256, K260, K262, K264, K266, K270, K272, K274, K276, K280, K282, K284, K286, K290, K3181, K5521, K625, K920, K921, K922
- Fractures
S02, S12, S22, S32, S42, S52, S62, S72, S82, S92, T02, T08, T10, T12, T14.2
- Falls
W00-W19
- Intracranial hemorrhage
I60, I61, I62, I690, I691, I692, S064, S065, S066, S068
- Suicide attempt, self-harm
T40 Poisoning by narcotics and psychodysleptics [hallucinogens]
T41 Poisoning by anaesthetics and therapeutic gases
T42 Poisoning by antiepileptic, sedative-hypnotic and antiparkinsonism drugs
T43 Poisoning by psychotropic drugs, not elsewhere classified
T54 Toxic effect of corrosive substances
T60 Toxic effect of pesticides
X60-X84 intentional self-harm
- Myocardial infarction
I21.9, I21.4, I21.0, I21.1, I21.2, I21.3, I22.0A, I22.0B, I22.0C, I22.8A, I22.8B, I22.8C, I22.8D, I22.8E, I22.8F, I22.8G, I22.8H, I22.8I, I22.8, I22.9, I22.1A, I22.1B, I22.1C
- Epilepsy/seizures
G40.XX
- Stroke
 - Transient ischemic attack
G459, I63, I693
 - Hemorrhagic stroke
I60, I61, I62, I690, I691, I692
 - Ischemic stroke
I63

[NOTE] Hospitalization and CT or MRI codes such as brain CT or MRI procedure code for ischemic stroke and hemorrhagic stroke, or any CT or MRI for systemic embolism are also required for identification.

- Brain CT
HA441, HA451, HA461, HA471, HA851
- Brain MRI
HE101, HE102, HE135, HE201, HE202, HE235, HE301, HE302, HE401, HE402, HE501, HE502, HE535
- Any CT or MRI or CT

HA401-HA416, HA424, HA425, HA434, HA435, HA443-HA449, HA453, HA456-HA459, HA463-HA469, HA473-HA479, HA496, HA497, HA801, HA805, HA809, HA813, HA834, HA835, HA853, HA856, HA857-HA859, S852

- MRI
HE103-HE142, HE203-HE234, HE236-HE241, HE303-HE334, HE403-HE434, HE430-HE434, HE503-HE534, HE536-HE541, HF101, HF102, HF104-HF107, HF201, HF202, HF305, HF306
- Hyponatremia
Will be identified by prescription codes for vasopressin receptor antagonists such as tolvaptan (drug code=616501ATB)

CC
I

[figure not shown]

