7. RATIONALE AND BACKGROUND

Major depressive disorder (MDD) is a prevalent disorder, causing great disability in affected individuals.¹⁻³ Its lifetime prevalence is estimated at 6.7% in Korea, and has continued to increase gradually since 2006.⁴ The approximate economic cost of MDD in 2005 was at \$4.5 billion, with indirect cost of \$2.96 billion due to loss of work productivity.⁵

Current guidelines recommend antidepressants like selective serotonin reuptake inhibitors (SSRIs) and selective serotonin norepinephrine reuptake inhibitors (SNRIs) as first-line pharmacotherapy for the management of MDD.⁶⁻⁷ The antidepressant effect not only reduces depressive symptoms but also contributes to patient's overall functional improvement.⁸ Despite plenty of available evidences on antidepressant therapy, Sequenced Treatment Alternatives to Relieve Depression (STAR*D) study showed that only about 30% of patients achieve remission with first-line treatment.⁹ In addition, those patients switching antidepressants compared to those initiating or maintaining first-line antidepressant therapy have different patient characteristics in terms of severity of depressive symptoms, anxiety, worse health-related quality of life, functional impairment.¹⁰ Non-adherence rates are high in MDD, which can lead to suboptimal treatment outcomes.¹¹

While there are many antidepressants from which physicians can select based on efficacy and tolerability profile, evidence on effectiveness and safety outcomes of new

antidepressants in real clinical practice among Korean MDD population is limited. Ahn *et al.* (2011) reported that antidepressant adherence among the Korean patients with MDD is less than 50% and recurrence and deterioration of MDD occurs due to the low adherence in Korea.¹² In addition, it is uncertain how patients are being properly managed with index medications and the proportion of switching, combination, and augmentation therapy during both acute and maintenance phases. And medication adherence and persistence rates are clinically important as they can have a major impact on the outcomes such as recurrence and recovery from depressive symptoms.

Therefore, the aim of this study is to investigate medication utilization pattern and risk of adverse outcomes among commonly used antidepressants by using nationwide claims database, in order to assess overall clinical benefit of antidepressant therapy in real-world practice.

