2.1 STUDY DESIGN

Retrospective cohort study design is used on Subjects who newly initiated antidepressant therapies between Jan 01, 2018 to Jun 30, 2019 in the Health Insurance Review and Service (HIRA) database

**Index date is the first prescription date of study drugs, including SSRIs, SNRIs, and other ADs during the intake period (Jan 01, 2018 to Jun 30, 2019)*

Using a retrospective cohort design, this study will evaluate treatment utilization pattern, medication compliance, incidence of recurrence, risk of adverse outcomes of antidepressant therapy, choice of therapy in various comorbidities, and choice of therapy in other specialty that are recorded in national health insurance database.

Figure 1. Study Design scheme

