**Study population**

Subjects who newly initiated antidepressant therapies between Jan 01, 2018 to Jun 30, 2019 in the Health Insurance Review and Service (HIRA) database

PFIZER CONFIDENTIAL

* Index date is the first prescription date of study drugs, including SSRIs, SNRIs, and other ADs during the intake period (Jan 01, 2018 to Jun 30, 2019).

Data source

The Korean HIRA claims data covers 97% of Korean population (about 50 million people) in the Korean National Health Insurance and 3% of Korean population in Medical Aid program.

HIRA claims database from January 01, 2017 to December 31, 2020 will be used for the analysis. It contains the data of universal health insurance system in Korea, wherein patient demographic information, inpatient and outpatient service use, pharmacy dispensing claims, and death can be obtained.

[figure not shown]
The main limitation of HIRA data is lack of clinical lab data and other clinical markers since it is a data collected for claims for reimbursement purpose.

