5.1 EFFICACY/EFFECTIVENESS ENDPOINT(S)

Medication compliance (persistence, discontinuation, adherence) along with recurrence are main primary efficacy endpoints and they are defined as follows:

1. MPR (medication possession ratio)
For each of 11 study drugs, the MPR will be calculated by (Days of medication possession from the prescriptions filled in the 180 days) / (180 days + extra days of drug supply from the last prescription fill during the 180 days)
2. Persistence
For each of 11 study drugs, the average length of treatment on the index drug during the first 180 day period (allowing 14 day permissible gap) will be

PFIZER CONFIDENTIAL

calculated. Switching, combination, augmentation, discontinuation will terminate the persistent period.

3. Discontinuation

For each of 11 study drugs chosen as index drug, the percentage of discontinuation in the first 90 days from the index date (acute treatment phase) will be measured (allowing 14 day permissible gap)

4. Adherence

For each of 11 study drugs chosen as index drug, adherence will be measured by MPR and persistence during the first 90 day and 180 day from the index date, respectively (acute treatment phase). MPR ≥ 0.75 and persistence ≥ 90 will be considered as adherence.

* For those period with any identified adverse outcome such as GI bleeding will be considered as a non-adherent period.

5. Recurrence

Recurrence during the acute treatment phase was operationally defined as either one of the following being satisfied:

- 1) Inpatient episode with a diagnosis code in Table 1
- 2) Inpatient episodes via the department of psychiatry or emergency medicine
- 3) Inpatient episode via nursing hospital
- 4) Emergency room visit with a diagnosis code in Table 1
- 5) Suicide attempt identified by the following KCD-7 codes:
 - T40 Poisoning by narcotics and psychodysleptics [hallucinogens]
 - T41 Poisoning by anaesthetics and therapeutic gases
 - T42 Poisoning by antiepileptic, sedative-hypnotic and antiparkinsonism drugs
 - T43 Poisoning by psychotropic drugs, not elsewhere classified
 - T54 Toxic effect of corrosive substances
 - T60 Toxic effect of pesticides
 - X60-X84 intentional self harm
- 6) Augmentation of the following non-AD drugs
 - Antipsychotic: amisulpride, aripiprazole, olanzapine, quetiapine, risperidone, perphenazine
 - Anticonvulsant: carbamazepine, valproic acid, lamotrigine
 - Mood stabilizer: lithium
 - Anxiolytic: buspirone
 - Thyroid hormone: levothyroxine, liothyronine

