7 STATISTICAL METHODOLOGY AND STATISTICAL ANALYSES

7.1 STATISTICAL METHODS

Means, medians, and standard deviations will be provided for continuous variables when performing descriptive analysis of continuous data. Numbers and percentages will be provided for dichotomous and polychotomous variables when performing descriptive analysis of categorical data. Bivariate comparisons of baseline characteristics and outcomes measures will be provided. Appropriate tests (e.g., t-test, chi-square test) will be used based on the distribution of the measure. The cumulative incidence rate for clinical outcomes (major bleeding event, and stroke) will be calculated. The incidence rate will be calculated as the number of patients who experience the event divided by the observed time at risk. An unadjusted Kaplan Meier curve will be drawn to illustrate time-to-event.

PFIZER CONFIDENTIAL

[figure not shown]
The propensity score matching (PSM) technique and the propensity score weighting technique will be used to control for confounders when comparing the antidepressants. After PSM, no significant differences are expected among all pre-index measures between the antidepressant cohorts except for clinical indication differences. Also covariates in Table 3 will be included in multivariate logistic regression framework for each antidepressant choice (binary variable of 1 for choice and 0 for no choice). Covariates will include variables such as age, geographic region, CCI score, and comorbidities. Non-pharmacologic treatments will be used as a covariate if dependent variable is adherence, persistence, or discontinuation since a previous study reported accompanying number of non-pharmacologic treatments significantly increase adherence of antidepressants (Ahn J et al., 2011). The final lists of variables to be used in the model will be discussed and determined during analysis development, after reviewing the pre-matched descriptive tables and post-matched pre-index measures. All data analysis will be executed using statistical software SAS version 9.4 or later.

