7.2.2 Study Drug Analysis in Maintenance Phase

- To understand the top 11 antidepressants usage among the Korean patients with depression in maintenance treatment phase
- Primary analysis
- Endpoints:
 - Choice of study drug
 - Average length of new treatment maintenance
 - Average number of co-medications (e.g., atypical antipsychotics, mood stabilizer, thyroid hormone, psychostimulant) when following changes occur from initial monotherapy: switching, combination, augmentation
 - Medication compliance (adherence, discontinuation, and persistence)
 - Recurrence by each antidepressant, by compliance
 - Risk of adverse events
- Population: patients from the acute treatment phase who started maintenance treatment (after 90 days from the index date)
- Significance on continuous variables will be tested by ANOVA (if equal variance condition satisfied) or Kruskal-Wallis H test (otherwise). Provider specialty and other patient characteristics will be used to fit antidepressant choice by multivariate logistic regression analysis of each study drug choice.
- Covariates: antidepressant class covariates such as SSRIs, SNRIs, and other ADs will be used as grouping variables.
- Missing values will be dropped from the analysis
- The role of this analysis is to provide information on study antidepressants in the maintenance phase of drug therapy for Korean patients with depression.

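### Time at risk and end of exposure are undefined for the primary adverse outcomes, and SAP 4.2/5.2 conflict with 2.2/7.2.2 on who is analysed and from when

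*SAP*

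**What the plan says.** Adverse outcomes are primary endpoints. SAP 5.2 describes them as "defined by KCD-7 diagnosis codes and/or NHI procedure codes appearing in medical claims data after the index date". A start is implied; no end is given.

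On the denominator, SAP 7.1 states: "The incidence rate will be calculated as the number of patients who experience the event divided by the observed time at risk". It does not say when that time starts, when it ends or what censors it. Protocol 9.7 adds only that safety outcomes come from time-to-event models.

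SAP 4.2 equates the safety set with the full analysis set. SAP 2.2, however, places adverse-outcome risk under the maintenance-phase objective, and SAP 7.2.2, which lists risk of adverse events as an endpoint, is run in "patients from the acute treatment phase who started maintenance treatment (after 90 days from the index date").

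The SAP does have a rule for the end of index treatment. Section 5.1 measures "the average length of treatment on the index drug during the first 180 day period (allowing 14 day permissible gap") and adds: "Switching, combination, augmentation, discontinuation will terminate the persistent period". That rule is applied to persistence only.

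**The concern.** The stated aim is to compare treatment-related outcomes between individual antidepressants. For that, each event and each day at risk must be tied to a drug. If follow-up simply runs on, events that occur off treatment, or on a second antidepressant, are mixed into the comparison of first drugs. The protocol itself expects this to be common: it describes switching, combination and augmentation, and reports that "antidepressant adherence among the Korean patients with MDD is less than 50" per cent.

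The population conflict is a separate problem. An event on day 40 counts under 5.2. Under 7.2.2 it is dropped if counting starts at day 91. If counting starts at index, it is kept only when the patient still went on to maintenance. Patients whose early event ended treatment disappear, and the first 90 days become time in which nobody in the analysis could have died or stopped for good.

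Two programmers following this SAP could therefore produce materially different primary safety rates. SAP section 1 records that the plan was amended during data analysis, so an open window could be settled after results are seen.

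**Working it through.** The plan gives no person-time, event count or time on drug, so there is no stated figure to reproduce. The check uses the SAP's dates plus stated assumptions.

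**1. The sections side by side**

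| Item | SAP 4.2 / 5.2 | SAP 2.2 / 7.2.2 |
|---|---|---|
| Population | Full analysis set | Patients who started maintenance after day 90 |
| Start of counting | After the index date | Maintenance phase; start of person-time not stated |
| End of counting | Not stated | Not stated (days 91 to 180 are defined in Table 3 for drug utilization only) |
| Event on day 40 | Counted | Dropped, or counted only if maintenance followed |

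**2. Length of follow-up if it runs to the end of data**

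Index dates fall "during the intake period (Jan 01, 2018 to Jun 30, 2019"). The end of data comes from SAP 2.1: "HIRA claims database from January 01, 2017 to December 31, 2020 will be used for the analysis".

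- Longest: 1 January 2018 to 31 December 2020 = 1,095 days.
- Shortest: 30 June 2019 to 31 December 2020 = 550 days.
- Mean, assuming uniform entry and no death or loss: (1,095 + 550) / 2 = 822.5 days.

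**3. Off-drug share over full follow-up, cohorts fixed by index drug**

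Time on drug T is not given. Assume it is exponential with median m, so the rate is λ = ln 2 / m. With follow-up F, off-drug share = 1 − E[min(T, F)] / 822.5, where E[min(T, F)] is (1 − e^(−λF)) / λ averaged over F.

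- m = 90 days: mean time on drug about 129 days; 1 − 129/822.5 = 84%.
- m = 180 days: about 247 days; 1 − 247/822.5 = 70%.
- Wider range: 95% at m = 30, 59% at m = 270, 50% at m = 365, 39% at m = 540.

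The break-even is a mean of 822.5 / 2 = 411 days on drug, or a median of about 365 days.

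**4. Off-drug share over days 91 to 180, patients still on the index drug at day 90**

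Off-drug share = 1 − (1 − e^(−90λ)) / (90λ).

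- m = 90: 1 − 0.500/0.693 = 28%.
- m = 180: 1 − 0.293/0.347 = 16%.

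The SAP does not say that starting maintenance means still being on the index drug. Without that condition the shares in the same window are 64% and 40%. Those figures include patients who stopped all treatment, so they are upper bounds.

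**5. Effect on a hazard ratio**

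For an on-drug ratio of 2.0, constant hazard and no excess off drug, the apparent ratio is 2.0 × on-share + 1.0 × off-share.

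| Window | m = 90 | m = 180 |
|---|---|---|
| Index to 31 December 2020 | 2.0 × 0.16 + 0.84 = 1.16 | 2.0 × 0.30 + 0.70 = 1.30 |
| Days 91 to 180, on drug at day 90 | 2.0 × 0.72 + 0.28 = 1.72 | 2.0 × 0.84 + 0.16 = 1.84 |

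**6. Immortal time**

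If patients are selected for starting maintenance after day 90 but person-time is counted from index, each contributes 90 guaranteed days. That is 90/822.5 = 11% of mean follow-up to the end of data, or 90/180 = 50% if counting stops at day 180.

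**The case against.** The strongest reply is that silence is not a rule. The sentence in 5.2 introduces code lists for what counts as an event and need not set follow-up. The undefined denominator in 7.1 is compatible with an on-treatment analysis. Grouping by index drug is stated for the acute-phase analysis in 7.2.1 and not repeated for adverse outcomes in 7.2.2. Figure 1 is not available, and text between 5.2 and 5.4 is blacked out.

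Much of this stands, and it rules out three stronger readings that a reader might infer:

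- *That most person-time charged to the index drug falls after it was stopped or switched.* The documents give no time on drug. Day 180 is where persistence measurement stops, not a maximum length of treatment, and the protocol's adherence figure is a proportion of patients, not a duration. The statement fails above a median of about 365 days, and in the narrower window of step 4 for patients still on drug at day 90.
- *That events are deliberately counted without limit and assigned to the first drug.* This is the natural reading, since 7.2.2 draws on patients classified by index drug and 7.1 matches cohorts on pre-index measures. It is not stated for safety.
- *That the bias is always toward no difference.* That needs equal risk off drug. If risks on the next drug, or stopping rates, differ between drugs, the bias can go either way. If events cluster early on treatment, the person-time share overstates the dilution.

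It is also fair to say that on-treatment censoring has its own weakness. Stopping is a post-baseline event, and propensity scores built on pre-index measures do not adjust for it. That is a reason to report both analyses, not to leave the choice open.

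**Conclusion.** The point holds as a gap and a conflict. No readable part of either document defines the end of exposure, the censoring or the time at risk for the primary adverse outcomes, and the SAP's sections disagree on population and start. Combining day-90 selection with counting from index would create immortal time.

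The size cannot be fixed from the documents. At the assumed medians of 90 to 180 days, a hazard ratio of 2.0 could appear as anything from about 1.16 to about 1.84, depending only on the window chosen and the time on drug. All of these rest on exponential time on drug, constant hazard and no off-drug excess; the full-follow-up figures also need uniform entry, no loss and cohorts fixed at index. That spread is wide enough that the window should be settled before the safety comparison is interpreted, and a null result should not be read as comparable safety until it is.

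**What to change.** **Time at risk (SAP 5.2 and 7.1).** Define on-treatment time at risk by reusing the 5.1 persistence rule: the 14-day gap, with discontinuation, switching, combination and augmentation ending exposure. If augmentation is not to censor, give the reason. Extend the rule past day 180, and end follow-up also at death or 31 December 2020. State that events are attributed to the index drug within this window.

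**Second analysis.** Report an all-follow-up analysis by index drug alongside it.

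**Population (SAP 2.2, 4.2, 5.2, 7.2.2).** Run the adverse-outcome analysis in the full analysis set from the index date. If a maintenance-phase analysis is kept to serve the stated objective, start both its events and its person-time at day 91, and say what starting maintenance means.

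**Cost.** SAP wording, plus programming to build treatment episodes beyond day 180. Events will be fewer: under the same assumptions, mean person-time falls from 822.5 days to about 129 days (median 90) or 247 days (median 180). Censoring at stop or switch may be informative; the all-follow-up analysis is the check on that.

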2.2 STUDY OBJECTIVES

Primary objectives:

1. Explore baseline characteristics and drug utilization patterns of 11 commonly used antidepressant therapy during 90 days of acute treatment phase
 - Top 11 commonly used antidepressants according to local market data are as follows:
 - Escitalopram, paroxetine, fluoxetine, mirtazapine, duloxetine, sertraline, venlafaxine, tianeptine, vortioxetine, desvenlafaxine, bupropion
 - Proportion of antidepressants prescribed by sex, age (<20, 21-64, > 65), sex and age combined
 - Initial doses used, average daily doses of each antidepressants
 - Average length of treatment with index medication before therapy change occurs (switching, combination, augmentation, discontinuation)
 - Adherence and persistence measured by medication possession ratio during first 90 days of treatment period
2. Explore drug utilization patterns such as therapy changes, medication compliance and recurrence relationship, and risk of adverse outcomes during maintenance phase
 - The choice of antidepressant, average length of new treatment maintenance, average number of co-administered medications (e.g., atypical antipsychotics, mood stabilizer, thyroid hormone, psychostimulant) when following changes occur from initial monotherapy:
 - Switching
 - Combination
 - Augmentation
 - Medication compliance and recurrence
 - Compliance measured as adherence and persistence
 - Recurrence
 - Relationship between recurrence and compliance

PFIZER CONFIDENTIAL

- *Risk of adverse outcomes measurement between individual ADs that are well known to be treatment-related (e.g., hyponatremia, GI bleeding, fractures, falls, risk of intracranial hemorrhage, attempted suicide/self-harm, myocardial infarction, epilepsy/seizures, stroke/transient ischemic stroke)*

Secondary objectives:

1. *Choice of antidepressants and drug utilization patterns in patients with various comorbidities*
 - *Psychiatric comorbidities*
 - *Mild cognitive impairment (MCI)*
2. *The relationship of non-pharmacologic treatment and discontinuation, medication compliance*
 - *Non-pharmacologic treatments may include: cognitive behavioral therapy (CBT), frequency of physician visit during acute and maintenance phase of treatment*
 - *Frequency of visit during the first 3 months of acute phase and its relationship to treatment maintenance at 4, 5, 6, 7, 8, 9 month time points and discontinuation rate*
3. *Choice of antidepressants by non-psychiatric specialty*

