4 ANALYSIS SETS/POPULATIONS

4.1 FULL ANALYSIS SET

Subjects who newly initiated antidepressant therapies between Jan 01, 2018 to Jun 30, 2019 in the Health Insurance Review and Service (HIRA) database

** Index date is the first prescription date of study drugs, including SSRIs, SNRIs, and other ADs during the intake period (Jan 01, 2018 to Jun 30, 2019).*

Inclusion criteria

Patients must meet all of the following inclusion criteria to be eligible for inclusion in the study:

1. *Patients aged 18 years or older and 70 years or younger on the index date*
2. *Patients who had at least one inpatient claim or two outpatient claims in the intake period with any of the following diagnosis codes:*

PFIZER CONFIDENTIAL

Table 1. Diagnosis Codes for Inclusion

KCD-7 Code ¹⁾	Description
F06.3	Organic mood[affective] disorders
F32*	Depressive episode
F33*	Recurrent depressive disorder
F34.1	Neurotic depression
F38.1	Other recurrent mood[affective] disorders
F41.2	Mixed anxiety and depressive disorder

1) KCD-7 = Korean version of ICD-10

3. Patients prescribed any of the following antidepressant during intake period (from January 1, 2018 to June 30, 2019)

Table 2. Study Drug List

Active Ingredient	Dosage	HIRA Drug Main Ingredient Codes
Escitalopram	5mg	474801ATB
	10mg	474802ATB
	20mg	474803ATB
	15mg	474804ATB
	10mg	521101ATD
	20mg	521102ATD
Paroxetine	10mg	209301ATB
	20mg	209302ATB
	12.5mg	209304ATR
	25mg	209305ATR
Fluoxetine	10mg	161501ACH
	10mg	161501ATB
	20mg	161502ACH
	20mg	161502ATB
	20mg	161502ATD
Mirtazapine	15mg	196201ATB
	15mg	196201ATD
	30mg	196202ATB
	30mg	196202ATD
	7.5mg	196204ATB
	7.5mg	196204ATD
Duloxetine	30mg	495501ACE
	30mg	495501ATE
	60mg	495502ACE
	60mg	495502ATE
Sertraline	50mg	227001ATB
	0.1g	227002ATB
Venlafaxine	75mg	247502ACR
	37.5mg	247504ACR
Tianeptine	12.5mg	229601ATB
Vortioxetine	5mg	628501ATB
	10mg	628502ATB
	15mg	628503ATB

PFIZER CONFIDENTIAL

	20mg	628504ATB
Desvenlafaxine	50mg 100mg	626401ATR 626402ATR
Bupropion	0.1g 0.15g 0.3g	428101ATB 428102ATR 428103ATR

Exclusion criteria

1. Patients meeting any of the following criteria will not be included in the study:
2. Patients with a claim of diagnosis codes in Table 1 during the 12 month pre-index period
3. Patients with a claim of prescription in Table 2 during the 12 month pre-index period

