4.2 SAFETY ANALYSIS SET

The safety analysis set is the same as the full analysis set.

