Recurrence	Primary outcome	HIRA Database	
Recurrence during the acute treatment phase was operationally defined as either one of the following being satisfied:
 
 1) inpatient episode with a diagnosis code in Table 1 2) inpatient episodes via the department of psychiatry or emergency medicine 3) inpatient episode via nursing hospital 4) emergency room visit with a diagnosis code in Table 1 5) suicide attempt identified by the following KCD-7 codes: 
 - T40 Poisoning by narcotics and psychodysleptics [hallucinogens] - T41 Poisoning by anaesthetics and therapeutic gases - T42 Poisoning by antiepileptic, sedative-hypnotic and antiparkinsonism drugs - T43 Poisoning by psychotropic drugs, not elsewhere classified - T54 Toxic effect of corrosive substances - T60 Toxic effect of pesticides - X60-X84 intentional self-harm 6) augmentation of the following non-AD drugs 
 - Antipsychotic amisulpride, aripiprazole, olanzapine, quetiapine, risperidone, perphenazine - Anticonvulsant carbamazepine, valproic acid, lamotrigine - Mood stabilizer lithium - Anxiolytic buspirone - Thyroid hormone levothyroxine, liothyronine 
Recurrence after the acute treatment phase was operationally defined as either one of the following being satisfied:
 
 1) ~6) the same as above 7) AD prescription after 30 days of drug holiday
Adverse outcomes	Primary outcome	HIRA Database	
The following known treatment related outcomes will be operationally defined by KCD-7 diagnosis codes and/or NHI procedure codes in medical claims
 
 - GI bleeding I850, I983, K2211, K226, K228, K250, K252, K254, K256, K260, K262, K264, K266, K270, K272, K274, K276, K280, K282, K284, K286, K290, K3181, K5521, K625, K920, K921, K922 - Fractures S02, S12, S22, S32, S42, S52, S62, S72, S82, S92, T02, T08, T10, T12, T14.2 - Falls W00-W19 - Intracranial hemorrhage

PFIZER CONFIDENTIAL

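### The primary adverse outcomes carry no new-event condition, so pre-existing disease can count as an on-study event, most clearly for epilepsy and for I69x codes outside the hospitalisation/imaging NOTE

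*SAP*

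**What the plan says.** SAP 5.2 makes adverse outcomes primary endpoints and identifies them by "KCD-7 diagnosis codes and/or NHI procedure codes appearing in medical claims data after the index date". SAP Table 3 (section 5.4) repeats the lists under this wording: "The following known treatment related outcomes will be operationally defined by KCD-7 diagnosis codes and/or NHI procedure codes in medical claims". Protocol 9.3, Table 3, defines the outcomes in the same way.

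The parts of the lists that matter here are:
- Epilepsy/seizures is G40.XX, with nothing further.
- Intracranial hemorrhage is "I60, I61, I62, I690, I691, I692, S064, S065, S066, S068".
- Within Stroke, the TIA list is G459, I63 and I693; hemorrhagic stroke is I60-I62 and I690-I692; ischemic stroke is I63.
- A NOTE after the stroke lists also requires hospitalisation and imaging, given as "brain CT or MRI procedure code for ischemic stroke and hemorrhagic stroke".
- Hyponatremia is identified by a prescription code for vasopressin receptor antagonists.

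SAP 4.1 has two look-back exclusions: "Patients with a claim of diagnosis codes in Table 1 during the 12 month pre-index period" and "Patients with a claim of prescription in Table 2 during the 12 month pre-index period". Tables 1 and 2 hold the depression codes and the study drugs. On the safety population, SAP 4.2 says: "The safety analysis set is the same as the full analysis set".

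**The concern.** Part of primary objective 2 is "Risk of adverse outcomes measurement between individual ADs that are well known to be treatment-related" (SAP 2.2). Protocol 9.7 estimates safety outcomes from time-to-event models, compares the 11 drugs on raw and on matched data, and sets p<0.05. SAP 7.1 divides patients with an event by observed time at risk. These are measures of new events, but the event rule also admits disease that was present before the drug was started.

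If such history is more common among starters of one drug, that drug's crude risk looks higher for a reason that precedes treatment. If history is balanced, it adds about the same number of non-events to every cohort and pulls ratios toward 1, which can hide a real difference. Propensity matching or weighting can balance history but cannot stop an old code from being counted. Balance on the relevant history is also not assured. The comorbidities in SAP Table 3 are psychiatric diagnoses, MCI and the Charlson index (components not listed); no adverse outcome is named as a covariate, and SAP 7.1 leaves the final covariate list open.

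There is a secondary effect. SAP 5.1 treats a period with an identified adverse outcome as non-adherent, so a carried-over code could also lower measured adherence.

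**Working it through.** The plan gives no figure to reproduce here. The check has four parts.

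**1. Is there a new-event condition anywhere?**
- SAP 5.2, SAP Table 3 and Protocol Table 3: code lists, no first-event wording.
- SAP 4.1 and Protocol 9.2.2: look-back on Tables 1 and 2 only. The other exclusions (Medical Aid, hospitalised at index, hospice) do not remove an outpatient with earlier disease.
- SAP 4.2: no event-free restriction.
- SAP 7.1: time at risk is not defined as starting event-free.
- SAP 7.2.2: lists adverse-event risk for patients who started maintenance after 90 days. It does not say how an event already coded in days 1-90 is handled.

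Result: none in the readable text.

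**2. Which codes are exposed?**
- G40.XX has no care-setting, treatment or imaging condition.
- All six hemorrhagic-stroke codes also sit in the intracranial hemorrhage list, a separate heading that the NOTE does not name. I690-I692 can therefore count there on the code alone.
- I693 appears only under TIA. The NOTE follows the whole stroke block but names only the ischemic and hemorrhagic subtypes, so its reach to TIA is unclear.
- I63, the entire ischemic-stroke list, is also in the TIA list, so those two subtypes are not distinct.

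**3. Is look-back available?** Data run from 1 Jan 2017 to 31 Dec 2020, and intake from 1 Jan 2018 to 30 Jun 2019 (SAP 2.1).
- Shortest look-back: 1 Jan 2017 to 1 Jan 2018 = 365 days.
- Time from index to the end of data: 550 days (index 30 Jun 2019) to 1,095 days (index 1 Jan 2018), which leaves ample time for a chronic diagnosis to be coded again.

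**4. Which way does the error go?** All inputs in this part are assumed, because the documents give no rates. Let c be the share of patients counted on a carried-over code and i the risk of a genuine new event, the same with or without history. Observed risk = c + (1-c)i. Let k be carried-over counts per new event, about c/i for small risks.

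- History balanced, true risk ratio 2: observed ratio = (2+k)/(1+k).
- No true effect, 1.5 times the carried-over codes in one drug: observed ratio = (1+1.5k)/(1+k).

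| k | True ratio 2 appears as | True ratio 1 appears as |
|---|---|---|
| 0.1 | 2.1/1.1 = 1.91 | 1.15/1.1 = 1.05 |
| 0.5 | 2.5/1.5 = 1.67 | 1.75/1.5 = 1.17 |
| 1 | 3/2 = 1.50 | 2.5/2 = 1.25 |
| 2 | 4/3 = 1.33 | 4/3 = 1.33 |

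A second assumed set, c = 0.2% to 1% with i = 0.05% to 0.2%, gives k from about 1 (0.002/0.002) to about 20 (0.01/0.0005). A true ratio of 2 then appears as 1.50 down to 1.05, and a true ratio of 1 as 1.25 up to 1.48. The spread between the two sets shows that only the direction can be taken from them.

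For risk differences with history balanced, observed/true = 1-c, which is 0.98 at c = 2%. With 1.5 times the carried-over codes in one drug, the difference is shifted by 0.5c(1-i).

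**The case against.** The strongest objections concern scope and weight.

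- **Not every listed code counts on its own.** A reader might infer that every adverse outcome is open to old disease in the same way. The text does not support that: ischemic and hemorrhagic stroke need hospitalisation and imaging, and hyponatremia needs a prescription. The NOTE is still not a prior-event rule, so the protection is partial.
- **The study is exploratory.** SAP section 3 gives no hypotheses or decision rules, and the objectives are to explore. This stands and lowers the priority, although Protocol 9.7 does plan p<0.05.
- **The plan is silent rather than wrong.** This is only partly so. Time at risk is undefined, but the event rule is stated, and following it counts old disease. SAP 7.1 names only major bleeding and stroke for cumulative incidence; epilepsy comes in through the general safety text of Protocol 9.7 and SAP 7.2.2.
- **A crude comparison of 11 drugs is confounded anyway, and matched data are planned beside it.** True, but dilution of the ratios survives matching.
- **Excluding prior fractures, falls, GI bleeding or self-harm discards genuine new events.** This stands and shapes the fix.
- **Sources.** Neither document says that I69x records sequelae of an earlier event; that is its meaning in ICD-10, of which SAP Table 1 says KCD-7 is the Korean version. The epilepsy example does not depend on it. Figure 1 and a redacted block after SAP 5.2 cannot be read, so the finding is limited to readable text.

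**Conclusion.** The point holds with limited scope. As written, the rule counts pre-existing disease as an on-study event, most clearly for epilepsy, then for I690-I692 under intracranial hemorrhage and arguably I693 under TIA. The direction is clear: ratios move toward 1 if history is balanced, and the raw comparison is biased if history differs by drug. The size is unknown.

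A reader might infer from the table that most counted events are old disease, or that the safety comparison is invalid. The documents do not support either reading: every k is assumed, k should be small where hospitalisation and imaging are required, and risk differences barely change under balance. For an exploratory study without decision rules this should be fixed, and the correction is cheap. The conclusion assumes that no prior-event condition sits in the unreadable parts and, for I69x only, that the codes carry their ICD-10 meaning.

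**What to change.** In SAP 5.2, Table 3 and 7.2.2:

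- (a) For epilepsy and the cerebrovascular outcomes, define the at-risk set as patients with no code from that outcome's list, including I69x, in the 12 months before the index date. Report, per outcome and drug, how many counted patients had a same-list code in the look-back; this replaces the assumed k with data.
- (b) Remove I690-I693 from the incident-event lists.
- (c) For fractures, falls, GI bleeding and self-harm, keep patients with prior events, adjust for or stratify by 12-month history, and give the history-free analysis as a sensitivity analysis.
- (d) For the maintenance analysis, date each event at its first post-index code, so that an acute-phase event coded again after day 90 is not counted as new. Report acute-phase events separately.
- (e) Minor: restrict the TIA subtype to G459 or label the list a TIA/ischemic stroke composite, and state whether the NOTE covers TIA and intracranial hemorrhage.

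The cost is code-list edits, a history flag per outcome and a re-run of the safety outputs, with no new data. The downsides are fewer events, wider intervals and history older than 12 months still missed. SAP section 1 records that the study is already in data analysis, so this change to a primary endpoint must be disclosed as made at that stage.
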